This study provides an opportunity to address a relevant clinical question, has the potential to impact SLE clinical care, and provides longitudinal blood specimens from well-characterized patients to potentially help identify biomarkers or explain mechanisms of disease flare. The goal of the trial is to obtain data comparing risks and benefits of continuing versus withdrawing MMF. The hope is that the study will provide physicians with some rationale for medical decision making. It is important to note that in practice the decision to withdraw from MMF is multifactorial; one has to weigh the increased risk of flare against decreased risk of lymphoproliferative disease, hematological derangements, and infections as well as the impact of chronic medication use on quality of life and plans for pregnancy. How the risks and benefits should be weighed is highly individual. The primary analysis, however, is designed to maximize the information available for decision making (Section 8.3.2.1, Primary Endpoint Analysis). Depending on the actual effect estimates, estimated confidence level, and level of acceptable risk, the results from this trial may or may not facilitate a decision regarding withdrawal for an individual patient, but should provide sufficient information for some clinical cases. Furthermore, the data will be of value for assessing feasibility and designing a larger more definitive trial, if such a trial were to be launched. In addition, this trial offers an opportunity to ask very practical questions about how results of mechanistic analyses might also guide clinical care, as well as core questions about the basis of the autoimmune process and the mechanism of action of MMF in SLE.

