### 2.2.2 Secondary Safety Objectives

• To describe the effect of MMF withdrawal on measures of safety and drug related toxicities.

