# 8.3.1 Safety Analysis

All safety analyses will be performed using the Safety Population.

AEs including changes in laboratory values will be graded according to the National Cancer Institute's *Common Terminology Criteria for Adverse Events (CTCAE) Version 4.0* (http://ctep.cancer.gov/reporting/ctc.html). The frequency of AEs will be summarized by system organ class, preferred term, severity (grade), and relationship to study treatment. Relationship to study treatment will be categorized as either treatment related (possibly, probably, or definitely related to study medication) or unrelated (unlikely related or unrelated). Similar analyses will be performed for SAEs. To account for differential duration of study participation among subjects, the summaries will include the event rate (i.e. number of events per person-time) in addition to the number and percent of events and subjects experiencing events.

For each key safety endpoint defined in Section 3.3.2, *Secondary Safety Endpoints* the proportion of subjects experiencing at least one event in each treatment group will be reported and the treatment groups compared based on Fisher's Exact Test. In addition, event rates in the two arms will be compared using Poisson regression.

Laboratory parameters will be summarized both overall and by treatment group using appropriate descriptive statistics. For each lab parameter, the number and percent of subjects that have an increase, decrease, or no change from baseline to Week 60 will be displayed for each treatment group and pooled across treatment arms. For parameters with an explicit NCI-CTCAE grading criterion, change from baseline will be indicated by a change in grade. For

parameters that do not have an explicit NCI-CTCAE, observed values will be categorized as 'high' (defined as >ULN) and 'normal' (defined as  $\leq$  ULN). Then, a change from baseline will be indicated as a change in category

[figure not shown]
All safety comparisons and associated p-values are considered exploratory, not as formal tests of hypothesis. As such, no adjustments will be made for multiple comparisons and all p-values must be interpreted cautiously.

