# 7.3.2. Probability of Experiencing a SELENA-SLEDAI Flare

**Endpoint**: The SELENA-SLEDAI instrument will be completed at baseline and every follow-up visit, including any Flare or Endpoint visits, during the course of the 60 week study period for all subjects. The SELENA-SLEDAI assesses SLE disease activity and flares based on changes in the SLEDAI score, the Physician's Global Assessment (PGA), medication use (prednisone, NSAIDS, Plaquenil, major immunosuppressives), other disease activity criteria, and hospitalization due to SLE. See Section 7.2.1., *Computation of the Primary Endpoint*, for more information on scoring of the SELENA-SLEDAI flare assessment.

For each subject, a yes/no variable will be created to indicate whether a subject had at least one mild/moderate or severe SELENA-SLEDAI flare by Week 60 and separately whether the subject had at least one severe SELENA-SLEDAI flare by Week 60. Subjects who terminate early from the study prior to experiencing any SELENA-SLEDAI flare will be categorized as not experiencing any SELENA-SLEDAI flare by Week 60.

Additionally, for each subject, the total number of visits with mild/moderate or severe SELENA-SLEDAI flares will be tabulated, including categorizing number of flare visits for a subject into 0, 1, or >1 flare.

The probability of experiencing any SELENA-SLEDAI flare and the probability of experiencing any severe SELENA-SLEDAI flare by Week 60 will be calculated in aggregate and within subgroups defined by disease manifestation (renal disease/extra-renal disease) and by baseline MMF dosing group (<2000 mg per day / ≥ 2000 mg per day).

**Analysis**: Analyses analogous to those specified for the primary endpoint (effect estimates and 95% confidence intervals, risk difference, and summaries of increased risk ( $\alpha$ ) vs.% confidence the "true" risk is  $\leq \alpha$ ) will be performed for the probability of experiencing any SELENA-SLEDAl flare and any severe SELENA-SLEDAl flare by Week 60, including analyses within subgroups for disease manifestation and baseline MMF dose. See Section 7.2.2, *Primary Analysis of the Primary Endpoint*, for more details on the analyses.

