#### 8. SAFETY EVALUATION

# 8.1. Overview of Safety Analysis Methods

All safety analyses will be carried out using the safety sample defined in Section 4.2 unless otherwise noted. Missing safety information will not be imputed. These analyses will not be stratified by site. All safety comparisons and associated p-values are considered exploratory, not as formal tests of hypothesis. As such, no adjustments will be made for multiple comparisons and all p-values must be interpreted cautiously.

Listings will be prepared for all safety measurements. All listings will be sorted in order of treatment, subject identifier (ID), and time of assessment (e.g., visit, time, and/or event).

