# 8.3.1. Secondary Safety Endpoints

Secondary safety endpoints include the following:

- 1. All Grade 3-5 adverse events, as defined by the NCI–CTCAE system, which are defined as possibly, probably, or definitely related to SLE.
- 2. All Grade 3-5 adverse events, as defined by the NCI-CTCAE system, which are defined as possibly, probably, or definitely related to MMF.
- 3. All NCI-CTCAE Grade 3-5 adverse events.
- 4. All serious adverse events.
- 5. All infection related events.
- 6. All malignancies.
- 7. All NCI-CTCAE Grade 3-5 hematological events.
- 8. Mortality possibly, probably, or definitely related to SLE.
- 9. All-cause mortality, defined as any death occurring at any time after randomization.

Serious adverse events will include only those events deemed serious per 21 CFR 312.32 (See Protocol Section 7.2.4). Events that require 24-hour reporting to the sponsor, such as BILAG A and severe SELENA-SLEDAI flares, will not be included unless they also meet SAE reporting criteria per 21 CFR 312.32; these events will be summarized separately.

Infections will include those events that are coded to the SOC of "Infections and infestations" along with any AE with an answer of Yes to the question "Was this AE an infection?" on the Adverse Events CRF page.

Malignancies will include those events that are coded to the SOC of "Neoplasms benign, malignant and unspecified (incl cysts and polyps)" along with any AE with an answer of Yes to the guestion "Was this AE a malignancy?" on the Adverse Events CRF page.

Hematological events will include AEs that are coded to the SOC of "Blood and lymphatic system disorders".

For each of the safety endpoints listed above, the AEs, classified by MedDRA system organ class and preferred term, will be summarized for each treatment group and overall. The

Version: 1.0 Page 32 of 48

summaries will include the event rate (i.e. number of events per person-time) in addition to the number and percent of events and subjects experiencing events.

The proportion of subjects experiencing at least one event specified above in each treatment group will be reported and the treatment groups compared based on Fisher's Exact Test. In addition, event rates in the two arms will be compared using Poisson regression.

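### The safety endpoints get per-arm summaries, a Fisher p-value and an event-rate comparison, but no pre-specified between-arm difference with a confidence interval

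*SAP*

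**What the plan says.** SAP 8.3.1 covers nine endpoints: Grade 3-5 adverse events overall, those related to SLE and those related to MMF, SAEs, infections, malignancies, Grade 3-5 hematological events, SLE-related death and death from any cause. Each arm's summary gives numbers and percentages of events and subjects, and the event rate per person-time. For the comparison, the proportion with at least one event "in each treatment group will be reported and the treatment groups compared based on Fisher's Exact Test", followed by "In addition, event rates in the two arms will be compared using Poisson regression". Protocol 8.3.1 has the same pair: "the treatment groups compared based on Fisher's Exact Test" and "event rates in the two arms will be compared using Poisson regression". Neither section names a between-arm difference, ratio or confidence interval.

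SAP 8.1 sets the status: "All safety comparisons and associated p-values are considered exploratory, not as formal tests of hypothesis". The 95% interval rule in SAP 7.3 stands under the disease activity endpoints and does not reach Section 8.

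The disease activity side is treated differently. For any SELENA-SLEDAI flare and any severe one, SAP 7.3.2 plans "Analyses analogous to those specified for the primary endpoint (effect estimates and 95% confidence intervals, risk difference, and summaries of increased risk" against confidence. SAP 7.3.4 (BILAG A), 7.3.5 (renal BILAG A) and 7.3.8 (escalation of therapy) do the same. SAP 7.3.7 gives a 95% interval for the between-arm difference in SLICC/DI change.

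The safety objective in Protocol 2.2.2 is "To describe the effect of MMF withdrawal on measures of safety and drug related toxicities". Protocol 1.5 states the trade-off: "one has to weigh the increased risk of flare against decreased risk of lymphoproliferative disease, hematological derangements, and infections".

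**The concern.** The trial exists to inform a trade-off. On one side, extra reactivation and flare risk is to be given as an absolute difference with an interval and a confidence curve. On the other side, infections and hematological events get two percentages, two rates and p-values. A p-value has no size and no direction of uncertainty, so it does not meet an objective of describing an effect.

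The practical risk is in the reading. With about 60 subjects per arm, a non-significant Fisher test is the usual result even for a difference that would matter to a patient. Without an interval beside it, such a result is easily taken as showing no infection benefit, or no excess of SAEs off MMF. Neither follows.

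**Working it through.** **Inputs.** 120 subjects, 1:1, so 60 per arm (Protocol 8.1). Maintenance risks of 0.05 to 0.15 and increases up to 0.15 are the Table 8.1 ranges; they concern reactivation and are borrowed here for scale. The 85% one-sided confidence level is also from Protocol 8.1. The documents give no expected adverse event rates for this population, so every safety rate and count below is an assumption.

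**The plan's own figure.** No figure is stated for the safety comparisons. The nearest is Table 8.1. For maintenance risk 0.05, increase 0.05 and acceptable increase 0.15, SE = sqrt(0.05×0.95/60 + 0.10×0.90/60) = 0.0479. Power = Φ((0.15 − 0.05)/0.0479 − 1.036) = Φ(1.05) = 0.854, against a stated 85%. All 22 cells reproduce within 2 points by this formula, so 60 per arm and the plan's own criterion are read correctly.

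**How often Fisher's test is non-significant.** With b(·; 60, p) the binomial probability, P(non-significant) = Σ b(i; 60, p1) b(j; 60, p0) over all pairs (i, j) with two-sided Fisher p ≥ 0.05. The last column gives the share of trials in which the 95% score (Miettinen-Nurminen) interval for the difference includes zero.

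| Maintenance | Withdrawal | Fisher non-significant | 95% score interval includes 0 |
|---|---|---|---|
| 0.05 | 0.15 | 67% | 54% |
| 0.10 | 0.20 | 75% | 68% |
| 0.15 | 0.25 | 80% | 73% |
| 0.05 | 0.20 | 37% | 27% |
| 0.10 | 0.25 | 51% | 42% |
| 0.15 | 0.30 | 58% | 50% |

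In the benefit direction, an infection risk of 0.30 on maintenance against 0.15 on withdrawal is non-significant 58% of the time, and 0.20 against 0.10 is non-significant 75% of the time.

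**What an interval adds.** Assumed numbers of subjects with an event, 60 per arm:

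| Withdrawal vs maintenance | Fisher p | Difference | 95% score interval | One-sided 85% upper limit |
|---|---|---|---|---|
| 10 vs 10 | 1.00 | 0.000 | -0.138 to 0.138 | 0.071 |
| 16 vs 10 | 0.27 | 0.100 | -0.049 to 0.248 | 0.178 |
| 9 vs 3 | 0.125 | 0.100 | -0.009 to 0.219 | 0.160 |
| 6 vs 10 | 0.42 | -0.067 | -0.196 to 0.059 | -0.002 |

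All four are non-significant, but they say different things. The first leaves room for an increase of about 14 points, the second for about 25. At the plan's 85% level the upper limits are 0.071 and 0.178, on opposite sides of 0.15.

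**The case against.** A reader might infer that the trial cannot say whether severe lupus is worse off MMF. The documents do not support that. Severe SELENA-SLEDAI flare, BILAG A flare, renal BILAG A flare and therapy escalation all get the full primary-style analysis. On the lupus side, the gap is limited to SLE-related Grade 3-5 adverse events and SLE-related death.

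The other points against are these.

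- **The difference can be derived.** Per-arm counts, percentages and person-time rates are reported, so the absolute difference is one subtraction. This stands: the interval is unplanned, not impossible. But its method, level and endpoints would then be chosen after the data are seen.
- **The comparisons are exploratory.** SAP 8.1 and Protocol 8.3.1 say so and ask for caution with the p-values. This stands, and it rules out calling Fisher's test an error in a confirmatory analysis. It also favors estimation, since Protocol 8.5.3 treats both p-values and intervals as descriptive, and safety is given only the first.
- **No acceptable increase is set for safety.** The quantity *a* is introduced for reactivation. The SAP carries the curve to flare and therapy endpoints, but not to adverse events. So the plan does not break its own framework by leaving the curve out here.
- **Low power comes from sample size.** This stands in large part: the score interval includes zero nearly as often as Fisher's test is non-significant. The gain lies in showing which differences remain compatible with the data, not in more frequent significance.
- **A crude score interval is not the current primary scale.** Both synopses name score intervals, but for the primary analysis, and SAP 7.2.2 and Section 12 now use Kaplan-Meier estimates. A crude proportion also ignores unequal follow-up. This stands, and is why the rate ratio with its interval belongs beside it.

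**Conclusion.** The point holds as a low-cost improvement. For the SAP 8.3.1 endpoints, the plan pre-specifies no subject-level effect estimate with an interval, and none is stated for the Poisson comparison. Under assumed maintenance risks of 0.05 to 0.15, Fisher's test would be non-significant in 67% to 80% of trials with a true 10-point increase, and in 37% to 58% with a 15-point increase. A p-value alone is therefore a poor description of the safety effect that readers are asked to weigh.

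These sizes assume 60 analyzed subjects per arm, independent binomial outcomes, complete follow-up and event rates that the documents do not give. Actual safety rates could lie outside the range. The point does not affect the primary analysis or the flare endpoints.

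**What to change.** In SAP 8.3.1:

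1. For each safety endpoint, report the withdrawal-minus-maintenance difference in the proportion of subjects with at least one event, with a 95% confidence interval. Name the method; a score interval is one suitable choice.
2. Report the Poisson result as a rate ratio with its 95% confidence interval, so that unequal follow-up is covered.
3. Keep Fisher's p-value as a supplement, and state that a non-significant result is not evidence of no difference.

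An upper-limit table or curve for SAEs and infections is optional, since no acceptable increase is defined for them.

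The cost is SAP wording and a few table columns, with no new data, subjects or visits. The downside is wide intervals that will look less reassuring than a non-significant p-value.

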# Study Arms:

- MMF maintenance arm: These subjects will continue MMF treatment (1000-3000 mg/day) for the rest of their study participation (up to Week 60).
- MMF withdrawal arm: These subjects will taper off MMF per the protocol-specified schedule over 12 weeks and remain off MMF for the rest of their study participation (up to Week 60 or until the primary endpoint of disease reactivation is met, whichever comes first).

**Study Design:** One hundred twenty eligible subjects will be randomized in a 1:1 ratio to one of the two study treatment arms – continuing MMF treatment for 60 weeks or tapering off MMF within 12 weeks. All subjects will continue on their anti-malarials and may continue the use of their corticosteroids.

Subject visits to assess endpoints will occur every 4 weeks from Day 0 through Week 24 and then at Weeks 32, 40, 48, and 60. As disease flares occur, subjects will be brought in for urgent, flare or endpoint visits to document symptoms, collect biological samples, and determine whether primary endpoint has been met.

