#### Secondary Mechanistic Assessments

- Levels of C3, C4, and anti-dsDNA at Baseline, Week 20, at the time of first flare, and immediately prior to first flare.
- Changes in levels of C3, C4, and anti-dsDNA from Baseline to Week 20, from Baseline to the time of first flare, and from Baseline to the time point immediately prior to first flare.
- Levels of antibodies to Sm, ribonucleoprotein (RNP), SSA/Ro, and SSB/La at Baseline.
- Changes in levels of antibodies to Sm, RNP, SSA/Ro, and SSB/La from Baseline to Week 60
- Levels of interferon-regulated chemokines at Baseline, Week 20, at the time of first flare, and time points immediately prior to and after first flare.
- Changes in levels of interferon-regulated chemokines from Baseline to Week 20, from Baseline to the time of first flare, and from Baseline to the time points immediately prior to and after first flare.
- Levels of inflammatory and other cytokines at Baseline, Week 20, at the time of first flare and at time points immediately prior to and after first flare.
- Changes in levels of inflammatory and other cytokines at Baseline, Week 20, at the time of first flare and at time points immediately prior to and after first flare.
- Presence/Absence of gene expression patterns (e.g. fingerprint or signature) at Baseline, Week 20, at time of first flare, and timepoints immediately prior to and after first flare.
- Change in gene expression patterns from Baseline to Week 20, from Baseline to the time of first flare, and from Baseline to the time points immediately prior to and after first flare.

**Sample Size:** 120 eligible subjects will be randomized within 24 months and each will be followed for up to Week 60, for a total study duration of 3 ¼ years.

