- AEs that lead to study drug discontinuation
- AEs with an outcome of death
- AEs that were reported as being related to MMF
- AEs that were reported as being related to SLE
- AEs reported by maximum severity
- AEs that are BILAG A flares
- AEs that are severe SELENA-SLEDAI flares

Version: 1.0 Page 31 of 48

In addition, AEs classified by MedDRA SOC and preferred term will be summarized for each treatment group and overall for each of the following:

- All AEs
- AEs by maximum severity
- AEs by relationship to study drug

Summary tables will present the total number of events as well as the number and percentage of subjects experiencing the events. If a subject experiences the same AE on multiple occasions, the event will be counted once for each occurrence when reporting the number of AEs. When reporting the number of subjects experiencing the events, a subject will only be counted once if they experience an event within the particular SOC or preferred term. Percentages will be based on the number of subjects in the safety population. To account for differential duration of study participation among subjects, the summaries will include the event rate (i.e. number of events per person-time) in addition to the number and percent of events and subjects experiencing events.

Separate data listings will be provided for treatment-related AEs and AEs leading to study drug discontinuation.

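### Recurrent adverse-event rates are compared by Poisson regression with no allowance for overdispersion; if the variance-to-mean ratio were 1.5 to 3, a nominal 5% comparison would run at about 11% to 26%

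*SAP*

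**What the plan says.** SAP 8.3.1 lists nine secondary safety endpoints. For each it plans two comparisons between arms. The first is at subject level: the proportion with at least one event is reported and "the treatment groups compared based on Fisher's Exact Test". The second is at event level: "event rates in the two arms will be compared using Poisson regression". Protocol 8.3.1 has the same pair.

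The event-level numerator includes repeats. When a subject has the same event more than once, SAP 8.3 says "the event will be counted once for each occurrence when reporting the number of AEs". The denominator is follow-up time; in SAP 8.3.1 the "summaries will include the event rate (i.e. number of events per person-time").

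Neither document mentions overdispersion, a scale parameter, a robust or clustered variance, or a negative binomial model. Neither gives an expected event rate, a variance, or a significance level for the safety comparisons.

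On their status, SAP 8.1 says "All safety comparisons and associated p-values are considered exploratory, not as formal tests of hypothesis". It continues that "no adjustments will be made for multiple comparisons and all p-values must be interpreted cautiously". The safety sections do not say that a rate ratio or its confidence interval will be reported.

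**The concern.** Poisson regression assumes that a subject's event count has variance equal to its mean. That fails if some patients are more event-prone than others, because repeat events then cluster in a few subjects. The point estimate is unaffected, but the standard error is too small and the p-value with it.

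The documents give reasons to expect such differences:
- Entry doses of MMF range from 1000 to 3000 mg/day, with corticosteroids permitted in some subjects (Protocol 4.1). Protocol 1.2.2 cites evidence that infection risk may be greater at the top of that dose range.
- Protocol 1.1 stresses how heterogeneous the disease is.
- The infection endpoint has no grade restriction, and events are recorded from Grade 2 upwards (Protocol 7.3.4) over as much as 60 weeks, so repeats in one subject are possible.

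At stake is the toxicity side of the decision the trial is meant to inform. Protocol 1.5 and 8.3.2.1 describe weighing flare risk against, among other things, infections and hematological harm. A rate comparison that looks more precise than it is would distort that weighing.

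**Working it through.** There is no planned figure to reproduce, because the documents state no rate, dispersion or power for this comparison. The check asks how a plain Poisson comparison behaves under assumed dispersion.

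**Inputs from the documents**
- Sample size: "One hundred twenty eligible subjects will be randomized in a 1:1 ratio to one of the two study treatment arms" (SAP section 1), so 60 per arm.
- Follow-up: "each will be followed for up to Week 60" (SAP section 1).
- Method and counting rule: as quoted above.

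**Assumptions**
- A two-sided 5% level.
- Variance-to-mean ratio φ. With gamma variation between patients (negative binomial, dispersion k) and mean count μ per subject, φ = 1 + kμ.

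**Step 1: formula.** If the true variance is φ times the mean, the Poisson standard error is too small by a factor of √φ. The true size of the nominal 5% Wald test is 2 × [1 − Φ(1.96/√φ)]. Coverage of a 95% interval, if one were reported, is one minus that.

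| φ | Standard error too small by | True size | Interval coverage |
|---|---|---|---|
| 1 | 1.00 | 5.0% | 95.0% |
| 1.25 | 1.12 | 8.0% | 92.0% |
| 1.5 | 1.22 | 11.0% | 89.0% |
| 2 | 1.41 | 16.6% | 83.4% |
| 3 | 1.73 | 25.8% | 74.2% |
| 4 | 2.00 | 32.7% | 67.3% |

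**Step 2: simulation at this trial's size.** 60 per arm, equal true rates, 20,000 replicates.

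| μ | k | φ | Plain Wald | Sandwich | Pearson-scaled |
|---|---|---|---|---|---|
| 0.5 | 1 | 1.5 | 10.2% | 5.7% | 5.1% |
| 1 | 0.5 | 1.5 | 11.0% | 5.9% | 5.4% |
| 1 | 1 | 2 | 16.4% | 5.6% | 5.0% |
| 1 | 2 | 3 | 25.7% | 6.5% | 5.7% |
| 2 | 1 | 3 | 25.6% | 6.0% | 5.4% |

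The simulation agrees with the formula. For all settings with μ of 0.25 or more and k from 0.5 to 2, the sandwich variance gives 4.9% to 6.5% and Pearson scaling 4.5% to 5.7%. With 15% dropout at μ = 1 and k = 1, the figures are 15.5% plain, 5.9% sandwich and 5.5% scaled.

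**Step 3: where the problem fades.**
- Sparse events (μ = 0.05 to 0.1, k from 0.5 to 2): φ is only 1.03 to 1.20 and the plain Wald size is 0.4% to 4.4%. A likelihood-ratio test would run at about 7% to 11%, but it already runs at 6.4% to 8.7% with no overdispersion, so most of that is small-sample error.
- Events that can occur only once per subject: for risks of 2% to 20% the plain Wald size is below 2.5%.

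**Step 4: the only event figures in the documents.** Protocol 1.2.2 quotes serious adverse events in 16.7% and infectious serious events in 7.0% of MMF-treated subjects in another trial, in moderate to severe disease. Reading these as proportions of subjects with an event (an assumption), negative binomial counts satisfy (1 + kμ)^(−1/k) = 1 − proportion.
- Serious events: k = 0.5 gives μ = 0.19 and φ = 1.10; k = 2 gives μ = 0.22 and φ = 1.44. Simulated plain Wald size is 5.2% to 9.2%.
- Infectious serious events: μ is 0.074 to 0.078 and φ is 1.04 to 1.16. Simulated size is 1.7% to 2.5%.

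No figure is given for all recorded infections or all Grade 3-5 events, which are likely to be more frequent.

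**The case against.** The best defence is that little hangs on these p-values. They are declared exploratory, no significance level is set, and no stopping or decision rule uses them: the guidance in Protocol 5.10.3 and 8.4 rests on counts in the withdrawal arm and on the risk difference for reactivation. Fisher's exact test on subjects is unaffected by repeat events and is reported for every endpoint, so a rate difference driven by a few patients would stand beside the subject counts.

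This stands as an argument about severity. It does not remove the problem. The caution in SAP 8.1 is tied to multiple comparisons and does not warn of a wrong variance. Fisher's test ignores repeat events and follow-up time; the Poisson comparison is the only planned between-arm safety analysis that uses them. A descriptive measure of evidence still needs the right standard error.

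Three stronger readings are tempting, and the documents support none of them:
- That the comparisons will run at 11% to 26%. That range is the formula evaluated at φ = 1.5 to 3. With no rate or dispersion in the documents, anything from about 5% to above 30% is open, and the serious-event figures in Protocol 1.2.2 point below 11%.
- That all nine endpoints are affected. Deaths cannot recur, and malignancies and similar categories are likely to be sparse.
- That the planned rate-ratio intervals are too narrow. None are specified; the 95% intervals in Protocol 8.3.2.2 and SAP 7.3 belong to the disease-activity analyses.

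**Conclusion.** The concern holds in conditional form. As written, the method understates the variance of recurrent-event counts whenever patients differ in their underlying rate. At an assumed ratio of 1.5 to 3 the error rate would be about two to five times nominal (11.0/5 = 2.2; 25.8/5 = 5.2), and any rate-ratio interval that was reported would be too narrow. The result rests on an assumed 5% level and an assumed dispersion.

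It bears chiefly on all infections and all Grade 3-5 events, and possibly on serious events. It does not bear on the two mortality endpoints, and hardly on sparse categories. Severity is minor, because the comparisons are exploratory and feed no decision rule.

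**What to change.** Amend SAP 8.3.1 so that, for endpoints that can recur, event rates are compared by Poisson regression with a robust (sandwich) or Pearson-scaled variance, or by negative binomial regression where counts allow, with log person-time as offset. Report the observed dispersion beside each comparison. Keep Fisher's exact test for all endpoints, and rely on it for mortality and sparse categories.

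The SAP should say in advance which endpoints count as sparse. The favourable results above cover means of 0.25 or more events per subject, that is about 30 events over both arms (120 × 0.25). At a mean of 0.02 (60 × 0.02 = 1.2 expected events per arm), the chance that at least one arm has no events is 1 − (1 − e^(−1.2))² = 51%, and the log rate ratio then has no finite estimate under either model.

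The cost is a few sentences in the SAP and a program option. The downside is somewhat larger p-values and, where intervals are reported, wider ones. The sandwich variance can also run slightly above nominal at 60 per arm (up to 6.5% in these simulations). If there is no overdispersion, little is lost.
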